5.2 Study Rationale

Given the progressive nature of CF, there is a strong rationale for treating patients earlier in life. Vertex is currently evaluating VX-659/TEZ/IVA TC therapy in Phase 3 studies in adult and adolescent CF subjects who are heterozygous for *F508del* with a second *CFTR* allele carrying a minimal function (MF) mutation that is not responsive to TEZ, IVA, or TEZ/IVA (F/MF genotypes; Appendix A) and subjects homozygous for *F508del* (F/F genotype). Given the clinical benefit seen in a Phase 2 study of adults with CF with VX-659/TEZ/IVA, the present study is designed to obtain pharmacokinetic (PK), safety, tolerability, and pharmacodynamic (PD) information to expand the evaluation of this study drug in the pediatric population 6 through 11 years of age with F/F or F/MF genotypes (refer to VX-659 Investigator's Brochure).

6 STUDY OBJECTIVES

6.1 Primary Objectives

Part A

To evaluate the PK of VX-659, TEZ, and IVA when dosed in TC

6.2 Secondary Objectives

Part A

- To evaluate the PK of TEZ and IVA metabolites
- To evaluate the safety and tolerability of VX-659/TEZ/IVA

7 STUDY ENDPOINTS

7.1 Primary Endpoints

Part A

PK parameters of VX-659, TEZ, and IVA, including $C_{\text{max}},\,C_{\text{trough}},$ and $AUC_{\text{0-}\tau}$

7.2 Secondary Endpoints

Part A

- PK parameters of TEZ and IVA metabolites, including C_{max}, C_{trough}, and AUC_{0-τ}
- Safety and tolerability as determined by AEs, clinical laboratory values, standard 12-lead ECGs, vital signs, and pulse oximetry

8 STUDY POPULATION

Eligibility will be reviewed and documented by a qualified member of the investigator's team before enrollment.

8.1 Inclusion Criteria

Parts A

Subjects who meet all of the following inclusion criteria will be eligible for Part A

- 1. Subject (or his or her legally appointed and authorized representative) will sign and date an informed consent form (ICF), and an assent form.
- 2. Subjects (males and/or females), 6 through 11 years of age, inclusive, on the date of informed consent.
- 3. Subjects who weigh ≥15 kg without shoes at the Screening Visit.

- 4. Confirmed diagnosis of CF as determined by the investigator.
- Subjects who are homozygous for F508del (F/F genotype) or heterozygous for F508del and a
 minimal function mutation that is not responsive to TEZ, IVA, or TEZ/IVA (F/MF
 genotypes; Appendix A).
 - Genotype should be confirmed at the Screening Visit.
 - If the screening *CFTR* genotype result is not received before the first dose of study drug, a previous *CFTR* genotype laboratory report may be used to establish eligibility.
 - Subjects who have been enrolled and whose screening genotype does not confirm study
 eligibility must be discontinued from the study (Section 9.9).
- Subjects with FEV₁ ≥40% of predicted normal for age, sex, and height using equations of the Global Lung Function Initiative (GLI)⁶ at the Screening Visit (Section 11.4.1).
- 7. Subjects with stable CF disease as deemed by the investigator at the Screening Visit.
- 8. Subjects who are willing to remain on a stable CF medication regimen (other than CFTR modulators) through Day 15 (**Part A**) or, if applicable, through the Safety Follow-up Visit.
- 9. Subjects who are able to swallow tablets.
- Female subjects of childbearing potential must have a negative serum pregnancy test at the Screening Visit.
- 11. Subjects of childbearing potential and who are sexually active must meet the contraception requirements outlined in Section 11.5.6.1.
- 12. As deemed by the investigator, the subject's legally appointed and authorized representative (e.g., parent or legal guardian) AND the subject must be able to understand protocol requirements, restrictions, and instructions. The subject's legally appointed and authorized representative should be able to ensure that the subject will comply with and is likely to complete the study as planned.

8.2 Exclusion Criteria

Parts A

Subjects who meet any of the following exclusion criteria will **not** be eligible for Part A

- History of any illness or any clinical condition that, in the opinion of the investigator, might confound the results of the study or pose an additional risk in administering study drug(s) to the subject. This includes, but is not limited to, the following:
- Clinically significant cirrhosis with or without portal hypertension
- Solid organ or hematological transplantation.
- Alcohol or drug abuse in the past year, including, but not limited to, cannabis, cocaine, and opiates, as deemed by the investigator.

- Cancer, except for squamous cell skin cancer, basal cell skin cancer, and Stage 0 cervical carcinoma in situ (all 3 with no recurrence for the last 5 years).
- Any clinically significant laboratory abnormalities at the Screening Visit that would interfere with the study assessments or pose an undue risk for the subject (as deemed by the investigator).
- 3. Any of the following abnormal laboratory values at screening:
 - Hemoglobin <10 g/dL
 - Total bilirubin $\ge 2 \times$ upper limit of normal (ULN)
 - Aspartate transaminase (AST), alanine transaminase (ALT), gamma-glutamyl transferase (GGT), or alkaline phosphatase (ALP) ≥3 × ULN
 - Abnormal renal function defined as glomerular filtration rate \leq 45 mL/min/1.73 m² (calculated by the Counahan-Barratt equation)⁷
- 4. An acute upper or lower respiratory infection, pulmonary exacerbation, or changes in therapy (including antibiotics) for pulmonary disease within 28 days before Day 1 (first dose of study drug).
- 5. Lung infection with organisms associated with a more rapid decline in pulmonary status (including, but not limited to, *Burkholderia cenocepacia*, *Burkholderia dolosa*, and *Mycobacterium abscessus*). For subjects who have had a history of a positive culture, the investigator will apply the following criteria to establish whether the subject is free of infection with such organisms:
 - The subject has not had a respiratory tract culture positive for these organisms within the 12 months before the date of informed consent and assent.
 - The subject has had at least 2 respiratory tract cultures negative for such organisms within the 12 months before the date of informed consent, with the first and last of these separated by at least 3 months, and the most recent one within the 6 months before the date of informed consent and assent.
- 6. An acute illness not related to CF (e.g., gastroenteritis) within 14 days before the first dose of study drug (Day 1).
- 7. A screen positive for drugs of abuse or alcohol, as defined in Section 11.5.2, at the Screening Visit.
- Ongoing or prior participation in an investigational drug study (including studies investigating VX-659 with or without coadminstration with other study drugs) within 30 days of the Screening Visit.
 - A washout period of 5 terminal half-lives of the previous investigational study drug, or 30 days, whichever is longer, must elapse before the Screening Visit.
 - The duration of the elapsed time may be longer if required by local regulations.
 Note: Ongoing participation in a noninterventional study (including observational studies) is permitted.

- 9. Use of restricted medication within specified duration before the first dose of study drug as defined in Table 9-2.
- 10. Female subjects who achieved menarche (had the first menstrual period) who are not willing to follow the contraception requirements outlined in Section 11.5.6.1.
- 11. The subject or a close relative of the subject is the investigator or a subinvestigator, research assistant, pharmacist, study coordinator, or other staff directly involved with the conduct of the study.

9 STUDY IMPLEMENTATION

9.1 Study Design

[figure not shown]
This is a Phase 3, 2-part (Parts A multicenter study evaluating the PK, safety, and tolerability of VX-659/TEZ/IVA TC therapy in CF (F/F and F/MF genotypes) subjects 6 through 11 years of age (inclusive).

Part A

A schematic of the study design for Part A is provided below. Approximately 12 subjects (F/F or F/MF genotypes) are planned for enrollment. During the Treatment Period, subjects will be administered VX-659/TEZ/IVA for approximately 15 days. A review of safety, tolerability, and available PK data will be completed by an internal Vertex team after Part A

Additional subjects may be enrolled as needed in Part A,

Figure 9-1 Part A Study Design

IVA: ivacaftor; n: number of subjects; TEZ: tezacaftor

VX-659/TEZ/IVA will be administered from Day 1 through Day 15. On Day 15, only the morning dose will be administered.

Table 9-1 Parts A

Subjects Weight	VX-659 Dose	TEZ Dose	IVA Dose
Part A			
All subjects	120 mg qd	$50 \mathrm{mg} \mathrm{qd}$	75 mg q12h

IVA: ivacaftor; qd: daily; q12h: every 12 hours; TEZ: tezacaftor

9.1.1 Screening

Parts A

Screening will occur within 28 days before administration of study drug. The investigator (or an appropriate authorized designee) will obtain informed consent and assent, if applicable, for each subject before any study procedure takes place.

Subjects previously screened for another Vertex study may participate in this study provided they meet the eligibility criteria (Section 8). Screening data from the previous study will be considered sufficient to satisfy the requirements of this study. Procedures required by this protocol will only be done if the procedures were not performed for the previous study. All

screening data from these subjects must be obtained within 28 days before administration of study drug.

To prepare for study participation, subjects will be instructed on the study restrictions (Section 9.4) and concomitant medications (Section 9.5).

9.1.1.1 Repetition of Screening Assessments

Screening assessments may be repeated once to establish study eligibility. If repeat values of the individual assessment(s) are within the eligibility criteria and completed within the screening window, then the subject is eligible for the study.

9.1.1.2 Rescreening

Subjects may be rescreened once. If a subject is rescreened, all screening assessments will be repeated, except for:

- *CFTR* genotyping
- Ophthalmologic examination (if performed within 3 months of the date of informed consent)

If a subject is rescreened, a new screening window will begin when the first rescreening assessment has been initiated.

9.1.1.3 Extension of Screening Period Window

Parts A

A subject may have the Screening Period window extended by 2 weeks for the following reasons:

- Repetition of the Screening Period assessments (Section 9.1.1.1)
- Unexpected operational or logistic delays, or to meet the eligibility criteria
- Scheduling of ophthalmologic examination (Section 11.5.5)

9.1.2 Treatment Period

Parts A

The Treatment Period will last approximately 15 days in Part A drug administration details are provided in Section 9.6.

Subjects who prematurely discontinue study drug treatment will remain in the study from the time of discontinuation of study drug treatment through the last scheduled study visit and complete the assessments for all study visits, as described in Section 9.1.4.

9.1.3 Follow-up

Part A

Subjects will have a Safety Follow-up Visit 28 (\pm 7) days after the last dose of study drug.

9.1.4 Early Termination of Treatment

Parts A

If a subject prematurely discontinues study drug treatment, an Early Termination of Treatment (ETT) Visit should be scheduled as soon as possible after the decision to discontinue treatment. Subjects who prematurely discontinue treatment will also be required to complete the Safety Follow-up Visit (Table 3-2 for Part A if applicable (Section 9.1.3).

If a subject withdraws from the study and also withdraws consent or assent, no further assessments will be performed. Vertex may retain and continue to use any data and samples collected before such withdrawal of consent or assent.

9.1.6 Completion of Study Participation

Completion of study participation for each individual subject is defined as 1 of the following:

Part A

- For subjects who complete the Treatment Period: the Safety Follow-up Visit
- For subjects who prematurely discontinue study drug treatment but do not withdraw consent (and assent, as applicable): the latest of the Day 15 Visit, ETT Visit, or Safety Follow-up Visit
- For subjects who withdraw consent or assent: date of withdrawal of consent or assent, whichever is earlier (Section 9.9)

9.2 Method of Assigning Subjects to Treatment Groups

An interactive web response system (IWRS) will be used.

9.3 Rationale for Study Elements

9.3.1 Study Design

The subjects studied are from the population that is expected to benefit from treatment with VX-659/TEZ/IVA.

Part A

The open-label design is considered adequate to evaluate the PK and safety of VX-659/TEZ/IVA in this pediatric population.

9.3.2 Study Population

Parts A

Patients with an F/MF genotype (30% of all patients with CF) generally have severe disease and do not have approved CFTR modulator therapy available to them; clinical studies of LUM/IVA and TEZ/IVA did not show improvement in lung function in this patient population. Without an available CFTR modulator therapy, patients with F/MF genotypes must continue to rely on adjunctive treatments and symptomatic therapies to manage their severe CF disease. Although the rate of decline in lung function is reduced in *F508del* homozygous patients treated with Orkambi⁸, this population has an inexorable decline in lung function. Based on in vitro data and preliminary clinical data, VX-659/TEZ/IVA is expected to provide a clinically relevant advantage over currently available treatments for F/MF and F/F patients.

Given the progressive nature of CF, there is a strong rationale for treating patients earlier in life. Experience with CFTR modulators in pediatric subjects ≥6 to ≤11 years of age, including with TEZ/IVA, suggests that the safety profile of VX-659/TEZ/IVA will be similar in children and adults, which supports evaluation of VX-659/TEZ/IVA in pediatric subjects in the present study.

9.3.3 Study Drug Dose and Duration

Parts A

VX-659 Dosage

A VX-659 dose of 240 mg once daily (qd) is currently under evaluation in ongoing Phase 3 studies of adult and adolescent (\geq 12 years of age) CF subjects with an F/MF or F/F genotype. The 240 mg dose was selected based on an assessment of the benefit-risk profile from Phase 2 Study VX16-659-101 (Study 659-101), which evaluated a range of VX-659 doses (80 mg qd, 240 mg qd, and 400 mg qd) in TC with TEZ/IVA in subjects with F/MF and F/F genotypes. In Study 659-101, the TC was generally safe and well tolerated in all VX-659 dose groups. Subjects with F/MF genotypes who received the VX-659 240 mg qd TC demonstrated a clinically meaningful improvement in ppFEV₁ (within-group mean [SE] absolute change of 11.6 [2.1] percentage points from baseline [P<0.0001], compared with a mean absolute change of 0.3 [2.8] percentage points in subjects who received placebo [P = 0.9053]). The improvement

in ppFEV₁ for VX-659 400 mg qd in TC with TEZ/IVA was similar to improvements for VX-659 240 mg qd.

The VX-659 dose of 120 mg qd selected for evaluation in the current study was determined based on population-PK modeling utilizing data from adults and simulating exposure over a range of body weights typical for a population of 6 to <12 year-olds, ranging from 15 to 50 kg. The simulations indicate that a dose of 120 mg qd is predicted to provide similar exposures to that observed in adults dosed with 240 mg qd, up to a body weight of approximately 40 kg. At a body weight of 40 kg or higher, exposure of VX-659 following dose of 120 mg is predicted to be low relative to that of adults dosed with 240 mg qd. At ≥40 kg, a dose of 240 mg qd is predicted to provide similar exposure to that of adults. A single dose level of 120 mg qd will be evaluated in Part A to confirm the appropriateness of the doses

Therefore, the dose selected for evaluation in Part A is predicted to be safe.

TEZ and IVA Dosages

TEZ will be administered as 50 mg qd and IVA will be administered as 75 mg every 12 hours (q12h) in all subjects in Part A

Part A

Duration of Dosing

The 15-day duration of dosing was chosen to provide an adequate assessment PK, safety, and tolerability of VX-659/TEZ/IVA

9.3.4 Rationale for Study Assessments

Parts A

The PK, safety, efficacy, and PD assessments are standard parameters for clinical studies in drug development and are generally recognized as reliable, accurate, and relevant to the study of subjects with CF. Ophthalmologic examinations were added to the standard safety assessments.

9.4 Study Restrictions

9.4.1 Prohibited Medications

Parts A

To avoid variable study results that may affect various metabolizing enzymes and transporters during in vivo studies (e.g., uncontrolled use of dietary/nutritional supplements), it is important to exclude subjects who do not comply with the study restrictions and prohibited medications summarized in Table 9-2.

Table 9-2 Prohibited Medications

	Timing of Restriction			
Medication	Start of Restriction	End of Restriction	Rationale	
Moderate and strong CYP3A or CYP2C9 inducers	None allowed within 14 days before the first dose of the study drug on Day 1	None allowed through completion of study participation	VX-659, TEZ, and IVA are metabolized extensively via CYP3A4. VX-659 is also metabolized by CYP2C9. Therefore, use of moderate and strong inducers of CYP3A or CYP2C9 and moderate and strong inhibitors of	
Moderate and strong CYP3A inhibitors (except ciprofloxacin) ^a	None allowed within 14 days before the first dose of the study drug on Day 1	None allowed through completion of study participation	CYP3A, which have the potential to alter the exposure of VX-659, TEZ, or IVA, will be prohibited.	
Sensitive OATP1B1 substrates	None allowed within 14 days before the first dose of the study drug on Day 1	None allowed through completion of study participation	VX-659 is a potential inhibitor of the hepatic transporter OATP1B1. Therefore, sensitive substrates of OATP1B1, such as HMG-CoA reductase inhibitors ("statins") are prohibited during treatment.	
CFTR modulators (investigational or approved), except for study drugs	None allowed within 28 days before the first dose of the study drug on Day 1	None allowed until after the last dose of study drug	These agents may confound the results of this study.	
Herbal and dietary supplements	None allowed within 14 days before the first dose of the study drug on Day 1	None allowed through completion of study participation	These agents may confound the results of this study.	

CYP: cytochrome P450; IVA: ivacaftor; OATP1B1: organic anion transporting polypeptide 1B1; TEZ: tezacaftor Ciprofloxacin is not a moderate CYP3A inhibitor on the basis of results of a drug-drug interaction study conducted with IVA, a sensitive CYP3A substrate (Kalydeco [ivacaftor] US Package Insert).

9.4.2 Exposure to Sunlight

Parts A

Subjects will take appropriate measures to minimize exposure to ultraviolet radiation (e.g., prolonged sunlight, tanning booths) from Day 1 through completion of study participation.

9.5 Prior and Concomitant Medications

Parts A

Prohibited medications as described in Section 9.4.1 are not allowed in this study while subjects are receiving study drug. A nonexhaustive study prohibitions and cautions list for food and medications will be provided in the Study Reference Manual.

9.6 Administration

9.6.1 Dosing

Part A

On Day 1 through Day 15, VX-659/TEZ/IVA will be orally administered with water. On Day 15, only the morning dose of VX-659/TEZ/IVA will be administered.

Study drug should be administered within approximately 30 minutes of the start of a fat-containing snack or meal, such as a standard "CF" meal or snack according to the following guidelines:

- 1. Morning dose of study drug will be administered at the site on Days 1, 2, 8, and 15.
- 2. Study drug will be administered after all predose assessments have been performed.
- 3. All doses of study drug (morning and evening, as applicable) should be administered at approximately every 12 hours (± 1 hour) on each dosing occasion (e.g., if the morning doses of study drug are administered at 08:00 hour on Day 1, all subsequent morning doses should be administered between 07:00 hour and 09:00 hour).
- 4. Study drug tablets will be administered within 5 minutes of each other.
- 5. Study drug will be administered with approximately 240 mL (approximately 1 cup, 8 ounces, or half a pint) of water.
- 6. At the Day 1 Visit, all subjects will be observed for 4 hours after the morning dose of the study drug.
- 7. The date, amount taken, and time of study drug administration including whether food was taken with each dose, will be recorded for 2 days before PK sample collection and on the days of PK sample collection.

9.6.2 Missed Doses

9.6.2.1 Morning Dose of Study Drug

Parts A

If a subject misses the morning dose of study drug and recalls within 6 hours, the subject should take his/her dose with food. If more than 6 hours but fewer than 12 hours have elapsed after his/her usual dosing time, the subject should take the morning dose of study drug but skip the evening dose of study drug. If more than 12 hours have elapsed after his/her usual dosing time, the subject should skip the morning dose of study drug and take the evening dose of study drug.

9.6.2.2 Evening Dose of Study Drug

Parts A

If a subject misses the evening dose of IVA and recalls within 6 hours, the subject should take his/her dose with food. If more than 6 hours have elapsed after his/her usual dosing time, the subject should skip that dose and resume his/her normal schedule for the following dose.

9.7 Dose Modification for Toxicity

Parts A

Modifications of the study drug dose are prohibited. Should any unacceptable toxicity arise, individual subjects will be withdrawn from the study and dosing will cease.

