9.9 Removal of Subjects

Parts A

Subjects may withdraw from the study at any time at their own request. Subjects may be withdrawn from study drug treatment at any time at the discretion of the investigator or Vertex for safety, behavior, noncompliance with study procedures, or administrative reasons. If a subject has been withdrawn from study drug treatment, the subject will continue to be followed, provided that the subject has not withdrawn consent (and assent, as applicable).

In addition, a subject must be discontinued from study drug treatment if the subject meets any of the following criteria:

- Has a screening CFTR genotype that does not confirm study eligibility if a previous CFTR genotype laboratory report was used to establish eligibility. These subjects must be discontinued from the study (Section 8.1)
- Meets any of the stopping (discontinuation) criteria (Section 9.8)
- Has a QTcF value above the threshold for repeat measurement (Section 11.5.4)
- Becomes pregnant (Section 11.5.6.2)

Subjects who discontinue study drug treatment should return for study assessments, as noted in Section 9.1.4.

If a subject does not return for a scheduled visit, reasonable effort will be made to contact the subject. In any circumstance, reasonable effort will be made to document subject outcome. The investigator will inquire about the reason for withdrawal, request that the subject return all unused investigational product(s), request that the subject return for an ETT Visit and Safety

Follow-up Visit, if applicable (see Section 9.1.4), and follow up with the subject regarding any unresolved AEs.

If the subject withdraws consent or assent for the study, no further assessments will be performed. Vertex may retain and continue using the study data and samples after the study is over, and may use the samples and information in the development of the study compound, and for other drugs and diagnostics, in publications and presentations, and for education purposes. If the subject withdraws from the study, the study data and samples collected will remain part of the study. A subject will not be able to request the withdrawal of his/her information from the study data. A subject may request destruction of the samples collected from him/her during the study as long as those samples can be identified as his/her samples.

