10.6 Compliance

Parts A

To ensure treatment compliance, the investigator or designee will supervise all study drug dosing that occurs at the site. At each visit, site personnel will review that the subject is compliant with study drug dosing and remind the subject of study drug dosing requirements. Compliance will also be assessed by ongoing study drug count.

If a subject demonstrates continued noncompliance of study drug dosing despite educational efforts, the investigator should consider discontinuing the subject from the study.

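### Section 9.7 takes a subject with unacceptable toxicity out of the study, whereas Sections 9.1.2, 9.1.4, 9.1.6 and 9.9 stop study drug and keep the subject in follow-up

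*Protocol*

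**What the plan says.** Section 9.7 prohibits dose modification and then tells the site what to do instead: "Should any unacceptable toxicity arise, individual subjects will be withdrawn from the study and dosing will cease". Leaving the study and ending dosing are stated as two separate consequences, and both are mandatory.

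The sections on discontinuation treat the same situation differently:

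- **Section 9.9** allows withdrawal from study drug treatment at the "discretion of the investigator or Vertex for safety, behavior, noncompliance with study procedures, or administrative reasons". It then adds: "If a subject has been withdrawn from study drug treatment, the subject will continue to be followed", provided consent, and assent where applicable, has not been withdrawn.
- **Section 9.1.2** says that subjects who stop drug early "will remain in the study from the time of discontinuation of study drug treatment through the last scheduled study visit".
- **Section 9.1.4** asks for an ETT Visit as soon as possible and continues: "Subjects who prematurely discontinue treatment will also be required to complete the Safety Follow-up Visit".
- **Section 9.1.6** sets the end of participation for these subjects, if consent stands, at whichever of the Day 15, ETT and Safety Follow-up Visits comes last.

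**The concern.** A site managing a child with toxicity finds two incompatible instructions. Section 9.7 is the section whose title names toxicity, so it is a natural place to look. It says the child leaves the study, while the other four sections say the child stays and is followed.

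The literal reading of 9.7 is plausible for two reasons. The sentence mentions the end of dosing separately, so leaving the study is hard to read as shorthand for stopping drug. The protocol also uses removal from the study deliberately elsewhere: Sections 8.1 and 9.9 require it when the screening genotype does not confirm eligibility, and 9.9 states this alongside the separate notion of stopping study drug.

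At stake is the off-drug safety follow-up of the subjects in whom it matters most. Safety and tolerability is a secondary objective of Part A, which enrolls about 12 subjects. One subject is therefore about 1/12 = 8% of the data. Section 9.10 provides for replacement only after withdrawals for nonsafety reasons, so a subject lost through toxicity would not be replaced.

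**Working it through.** The protocol gives no figure to reproduce. The check is a comparison of sections, followed by a count from Table 3-2.

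**1. What happens to a subject stopped for unacceptable toxicity who has not withdrawn consent or assent?**

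| Section | Study drug | Study participation |
|---|---|---|
| 9.7 | stops | withdrawn |
| 9.9 (safety withdrawal) | stops | followed |
| 9.1.2 | stops | stays through the last scheduled visit |
| 9.1.4 | stops | ETT and Safety Follow-up Visits |
| 9.1.6 | stops | ends at the latest of Day 15, ETT and Safety Follow-up |

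Sections 9.1.2, 9.1.4 and 9.1.6 make no exception for toxicity, and 9.9 names safety as a ground. Section 9.7 is the outlier.

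**2. Do the specific toxicity rules side with 9.7?** They do not. Section 9.8.1 discontinues study drug after a confirmed liver signal and requires monitoring until levels normalize or return to baseline, which presupposes a subject still under observation. Section 9.8.2 interrupts dosing for severe or serious rash. Section 11.5.4 ends dosing after a QTcF breach. None of them removes the subject from the study.

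**3. What ends assessments?** Section 9.1.4 says: "If a subject withdraws from the study and also withdraws consent or assent, no further assessments will be performed". The condition is withdrawal of consent or assent, in addition to leaving the study. Section 9.9 gives the same condition. Neither makes toxicity a reason to stop assessing the subject.

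**4. What would a literal reading of 9.7 cost?** Table 3-2, leaving out pregnancy tests and PK samples, marks six safety assessments at the Safety Follow-up Visit: physical examination, vital signs, pulse oximetry, ECG, serum chemistry and hematology. Per affected subject:

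- Site applies 9.1.2, 9.1.4 and 9.9: 0 assessments lost.
- Site follows 9.7 and drops only the Safety Follow-up Visit: 6 lost, including 1 chemistry, 1 hematology and 1 ECG.

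An expected loss would be the number of subjects with a toxicity stop, times the share of sites following 9.7, times the loss per subject. The protocol gives neither of the first two, so no expected loss is computed.

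**The case against.** The strongest reply is that the conflict is mostly one of terms. By Section 9.1.4, leaving the study does not by itself end assessments, because consent or assent must also be withdrawn. Section 9.1.6 has no completion category for a subject removed by the investigator or sponsor for toxicity, so such a subject still completes at the latest of the three visits. Section 9.9 also has the investigator "request that the subject return for an ETT Visit" and a Safety Follow-up Visit, and follow up unresolved adverse events. The defined liver, rash and QTcF rules act on study drug only, so just a discretionary stop outside them would fall under the loose sentence. All of this stands and keeps the point small. It does not remove the contradiction, since 9.7 is mandatory, carries no cross-reference to these sections, and says something different.

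A reader might also infer more than the protocol supports:

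- **That 9.7 shortens adverse event collection or the treatment-emergent period.** Adverse event collection (13.1.1.3) stops at completion of participation, and the treatment-emergent period (12.3.1) ends at the earlier of completion and 28 days after the last dose. Completion is fixed by 9.1.6, not by 9.7.
- **That many assessments are lost.** Adding the Day 15, ETT and Safety Follow-up marks gives 7 + 6 + 6 = 19 for a stop after the Day 8 Visit. This assumes that the site skips every remaining visit, including the ETT Visit due promptly after the decision to stop, and the starting point is arbitrary. It is not an estimate.
- **That Section 10.6 repeats the error.** After continued dosing noncompliance it says "the investigator should consider discontinuing the subject from the study". That is discretionary, and its ground is noncompliance with dosing, whereas 9.9 speaks of noncompliance with study procedures. It is a mismatch in wording, not a conflicting instruction.
- **That pharmacokinetics is wholly untouched.** Table 3-2 still calls for one PK sample at a PK visit after permanent discontinuation, and a literal reading of 9.7 could lose it. A single off-drug sample is unlikely to matter for the primary endpoint, but an unqualified statement would be wrong.

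**Conclusion.** The contradiction is real and 9.7 is wrong as written. It is minor. For a safety stop, the rest of the protocol consistently ends study drug and continues follow-up, and most sites would probably act accordingly.

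Even under a literal reading of 9.7, some safety information survives. The event that led to the stop is still a treatment-emergent adverse event (12.3.5.1) and is followed until the investigator gives a final outcome (13.1.1.7), and the subject stays in the Safety Set (12.2). What could be lost is the remaining scheduled monitoring, such as the Safety Follow-up chemistry, hematology and ECG.

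That loss depends on a toxicity stop occurring, on consent and assent remaining in place, and on the site putting 9.7 above four other sections. The frequency of the first and last is unknown. No analysis set, stopping criterion or planned analysis changes.

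**What to change.** In Section 9.7, replace the removal from the study and the end of dosing with: *withdrawn from study drug treatment and will continue to be followed as described in Sections 9.1.2, 9.1.4 and 9.9*.

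The cost is one sentence in the next amendment. Every visit concerned is already in Table 3-2, so no visit, procedure or stopping rule is added, and 9.1.6 and the treatment-emergent period definition need no change.

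Section 10.6 could be brought into line in the same amendment by referring to study drug treatment and to 9.9. That is optional editorial tidying and not part of this point.
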